11.0 Provisions to Monitor the Data to Ensure the Safety of Subjects

The PI will create a DSMB, comprised of multidisciplinary faculty with expertise in addiction-focused pharmacotherapy and behavioral treatment trials. The DSMB will meet annually (more frequently as needed for emergency situations) to review any AEs related to the study, as well as review of any data management related errors. The board may be called at any point if needed for SAEs, etc. Modification will be made in the procedures and/or the protocol if necessary, based on the findings of the board.

Reports provided to the DSMB on an annual basis will address the following areas: 1) the progress of the research study, including assessments of data quality and participant recruitment, accrual, and retention; 2) review of outcome and adverse event data to determine whether there is any change to anticipated benefit-to-risk ratio of study participation, and whether the study should continue as originally designed, should be changed, or should be terminated; 3) assessment of external factors or relevant information; and 4) review of study procedures designed to protect the privacy of the research participants and the confidentiality of their data. Following review of the annual update on the study, the DSMB will provide a written report that will be submitted annually with the IRB renewal.

Data will be collected by the appropriate individual (PI and/or designated research staff) and will only be identified with the study's ID of the participant. The codes linking the name of the participant to the study ID will be kept confidential in a secured cabinet by the PI or password-protected data file. Only the PI and designated research staff will have access to these files. Collected forms will be securely transported to the offices of the PI and designated research staff for data entry. Research staff will enter data in REDCap; a secure, web-based application designed exclusively to support data capture for research studies. REDCap provides: 1) an intuitive interface for data entry (with data validation); 2) audit trails for tracking data manipulation and export procedures; 3) automated export procedures for seamless data downloads to common statistical packages (SPSS, SAS); 4) procedures for importing data from external sources; and 5) advanced features, such as branching logic and calculated fields. These procedures are effective in minimizing data entry errors (e.g., missing or errant data). The smartphone application is equipped to transmit data immediately into REDCap. Data are transmitted from study devices and identified through subject IDs. Once data have been transmitted to the secure study server and web portal from the loaner iPhone or participant's personal smartphone, no personal information will be stored on the device. Any information that is stored on the phones will be de-identified. If the loaner iPhone is lost or stolen, devices will be reset immediately.

12.0 Withdrawal of Subjects

Participants will be informed that they may discontinue the study at any time without penalty and that they will be pro-rated for all completed research activities. Participants may also be withdrawn from the study by the PI if it is determined that it is in the participant's best interest (safety concern, requiring intervention) or due to the participant's noncompliance with the protocol.

13.0 Risks to Subjects

The risks associated with participation in this study include adverse events related to study medication (varenicline), nicotine withdrawal, and the potential loss of confidentiality. Potential risk details are

described below and the PI will ensure that all risks are clearly defined for study participants and are thoroughly understood during the informed consent process and throughout the study period.

Adverse Events Related to Study Medication. The informed consent process will be used to thoroughly educate participants about potential medication-related risks. Varencline is the medication being used in this study to support tobacco cessation. Several companies now offer varenicline in the US: 1) Chantix® (from Pfizer in the US: http://www.pfizer.com/files/products/uspi_chantix.pdf); 2) Apo-varenicline in Canada (authorized for use in the US by the FDA; https://www1.apotex.com/products/us/downloads/mon/apo_var_fct_mon.pdf, <https://www.fda.gov/media/150799/download>), 3) generic varenicline from Par Pharmaceuticals: https://www.parpharm.com/pdfs/catalog/generic/Varenicline_Tablets_PI_07-2021.pdf), and 4) generic varenicline from Glenmark Pharmaceuticals: <https://glenmarkpharma-us.com/varenicline-tablets/>. The risks associated with study medication (varenicline) are detailed in the informed consent document and will be discussed prior to enrollment. Specifically, it reports that “the most common adverse reactions (>5% and twice the rate seen in placebo-treated patients) were nausea, abnormal (e.g., vivid, unusual, or strange) dreams, constipation, flatulence, and vomiting.” While no serious or severe adverse events or interactions are expected to occur with varenicline, appropriate procedures are in place should participants experience adverse events related to varenicline administration. Rigorous screening procedures and exclusion criteria are designed to exclude potential participants at elevated risk for adverse events related to study medication. This includes comprehensive psychiatric assessment and evaluation to exclude individuals with currently unstable psychiatric and/or medical disorders. Designated medical and research personnel will conduct serial psychiatric and medical evaluations at screening and will be consulted as needed throughout the study to address any concerns that may arise. Comprehensive and detailed adverse event monitoring will be the responsibility of the entire research team. Adverse events related to this medication (e.g., nausea, vomiting, vivid dreams, constipation, neuropsychiatric events) are possible and will be assessed carefully throughout the study. The PI will be immediately contacted in the event of any emergencies and will guide the plan for addressing and managing the situation with the help of the designated medical clinicians on the study team. Participants experiencing intolerable adverse events will have the opportunity to reduce the dose of study medication or discontinue medication altogether, while remaining in the study for ongoing monitoring.

Loss of Confidentiality. There is the risk of breach of confidentiality. The research team has procedures in place to minimize the risk of any confidentiality breach. Participant records are stored in locked files within locked offices, or in password-protected databases. Much of the data collected is de-identified and uses a participant ID. No specific or general participant information will be left in public access areas, and no oral communication regarding participants with identifiers will be made in any public areas. Research staff members have been given extensive training in maintaining confidentiality as well as HIPAA regulations. Participants will be informed of these potential risks during the informed consent process and will have the option to leave the study at any point. In specific instances, participant PHI (name, etc.) may be available to other entities, such as for ClinCard registration/payment purposes.

Nicotine Withdrawal. Participants enrolled in the study will receive comprehensive tobacco cessation treatment and may reduce or abstain from tobacco use during the study period. Participants will be daily smokers, and as such, they may experience nicotine withdrawal symptoms and/or discomfort during their quit attempt. Nicotine withdrawal symptoms may include: anxiety, depressed mood, irritability, restlessness, sleep difficulty, strange dreams, increased appetite, headaches, tension, difficulty concentrating and general physical discomfort. There are no reports in the current literature of severe physiological or psychiatric consequences resulting from nicotine withdrawal. Participants will be informed of the potential discomfort they may experience during this brief period of abstinence and will be advised to contact research staff if they feel that their withdrawal symptoms worsen during the study.

Pregnancy. Participants who become pregnant during the trial will be instructed to discontinue study medication and withdrawn from the study. Participants will be encouraged to seek medical attention. The study team will be conducting pregnancy tests on all female participants at every visit to ensure safety. If participants are considering becoming pregnant within the next three months prior to study participation, then they will not be included into the study. We will also ask female participants to agree to use some form of birth control during the study as an additional precaution.

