Training Visit: At this training visit, participants will see an example medication video (on their own mobile device or a loaner smartphone) and complete it in office. After the training visit, participants will begin receiving daily medication videos, which they will be instructed to complete twice a day so as to prepare for Day 0. Participants will complete these medication videos twice a day through their week 12. This period constitutes a pre-quit monitoring lead-in prior to the dispensation of medication. Participants will receive a brief counseling session in preparation for their target quit date (Day 8).

Day 0: On Day 0, participants will be given their first week of varenicline. The standard dose titration schedule will be used, which includes 0.5 mg once per day (q.d.) on Days 1-3, 0.5 mg twice per day (b.i.d.) on Days 4-7, and 1.0 mg b.i.d. starting on Day 8. Dosing of 2.0 mg per day will be maintained for the next 11 weeks. They will be given contact information if they are experiencing adverse events, including an emergency number for after-hour issues with medication. Participants will be encouraged to contact study personnel at any time to address concerns. The medical clinician/Co-I will provide medical supervision for this study and designated medical clinicians will provide oversight for any adverse events. MUSC medical clinician(s) will have the ability to support non-Charleston based site staff with adverse events and other medical concerns remote via telephone, doxy.me, or other HIPAA-compliant, MUSC-IS approved platforms for telehealth. If a participant experiences intolerable medication-related adverse events, a dose reduction to 0.5 mg twice per day may be undertaken (temporary or permanent dose reduction depending on alleviation of symptoms). If the participant is unable to tolerate the reduced dose, the medication will be discontinued, and the participant will continue to be tracked. At this visit, participants will be reminded or retrained on how to upload videos of themselves taking their medication (twice daily) via REDCap. Medication to be used by non-Charleston study sites will be ordered through MUSC and shipped directly to research staff or directly to the participant's home via registered courier. Staff will store medication in a controlled access environment and only accessed by designated staff.

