contingency management) will be provided based on tobacco abstinence. Vitals will be obtained at weeks 4, 8, 12, or as needed throughout the study (any visit). Urine samples will be collected and separated for: 1) immediate tests conducted by research staff (cotinine, cannabinoids, pregnancy [weeks 4, 8, 12, or as needed], other drugs); and 2) delivery to the MUSC Charleston laboratory for quantitative urinary cotinine and cannabinoid (creatinine-normalized) assay runs. Staff will label and store urine samples (if not in Charleston) to be shipped to MUSC per laboratory protocols. A sub-sample of 10 participants who are cannabis co-users will also be asked to participate in a study addendum that includes the collection of a saliva sample to test for various cannabinoids. Participants will complete their end-of-treatment study visit (Week 12), and a follow-up visit at Week 26. Early termination (ET) visits (in-person or remote) may occur if a participant wishes to withdraw from the study. Week 12 assessments and procedures will be conducted for ET visits, should they occur.

Follow-up Phone Visit (Week 16): During this follow-up visit, participants will be contacted for a brief phone call to assess overall health, as well as current tobacco and cannabis use.

Follow-Up Visit (Week 26): During this final follow-up visit participants will complete self-report questionnaires (e.g., craving, withdrawal, etc.). Daily use of cigarettes, other substances, alcohol, and other tobacco will be gathered during the follow-up period.

Unscheduled Visit (PRN): Participants may be asked to return to the study office for unexpected incidental needs such as addressing a technological concern with the loaned study equipment (phone) or any other issue that cannot be resolved remotely. It is not anticipated that any supplemental data would be collected at these visits and they should take less than 15 minutes to complete.

If a participant has an unexpected conflict with attending a visit or the visit must be completed by staff remotely (e.g., transportation issue or travel), arrangements (i.e., phone visit) may be made to remotely complete visit procedures, in order to maintain data collection and study engagement. There is the potential, with proper planning, that participants may be able to complete urine needs at home. Participants will be given proper materials and properly instructed on how to collect/store urine while at home.

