
Secondary Data Analysis: In addition to end of treatment point prevalence tobacco abstinence rates, similar analytic models will be used to assess abstinence rates at the 6-month follow-up visit. Additionally, longitudinal analysis of weekly tobacco abstinence will be assessed using repeated measures logistic regression models using a general estimating equations framework (GEE) (115) and working correlation

structures will be independently compared using the quasi-likelihood under the independence model criterion statistic (116). Similarly, the number of smoking days per week and cigarettes per day will be collected via daily diaries and compared between co-use cohorts using generalized linear mixed effects regression models. Finally, weekly cannabis and tobacco use will be collected to develop group-based trajectory models and time naïve covariates will be used to determine group membership. Additionally, changes in cannabis craving, withdrawal, use, and subjective effects during treatment with varenicline will be examined in the cannabis co-use group. Specifically, changes in cannabis craving, withdrawal (synchronous effects of varenicline) and cannabis use severity (substitution) will be assessed for correlations with changes in tobacco use. Generalized linear mixed effects models will be developed with cannabis use outcomes and the time varying effects of tobacco use as the primary independent variable. Further, noting possible differences in the relationship between tobacco outcomes and combustible/non-combustible cannabis use, model effect modification will be assessed using cannabis use type groupings (primarily combustible vs. primarily non-combustible). All analyses will be conducted using SAS version 9.4 (SAS Institute, Cary, NC, USA).

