Missing data and attrition. The study team has procedures in place to minimize missing data and attrition (e.g., reminders, compensation, updated and detailed locator information, etc.); however, these methods do not ensure that all data will be collected. Appropriate analysis methods will be employed to accommodate missing data. Methods of maximum likelihood yield valid inferences assuming ignorable attrition (i.e., attrition is accounted for by covariates or the dependent variable measured prior to dropout). In addition, in keeping with the Intent to Treat Principle, we will make every effort to continue assessments for the entire course of treatment, even among those who stop participating in study procedures.

Data Management. Data will be collected by trained and approved research staff and will only be identified with the study's ID of the participant. The codes linking the name of the participant to the study ID will be kept confidential in a secured cabinet or password-protected data file. Collected study forms will be kept within the office suite of the PI and research staff (Charleston) and within research office suites at participating sites and will not be taken outside of any office buildings. Research staff will enter data into a database management system maintained by MUSC, Research Electronic Data Capture (REDCap). REDCap is a secure, web-based application designed exclusively to support data capture for research studies. These procedures are effective in minimizing data entry errors (e.g., missing or errant data). Direct entry of data by study participants (self-reports) will also be conducted in this study. This is done through a front-end survey interface that allows the participant to enter data on select questionnaires/assessments, but not access any other study records or data in REDCap. A REDCap survey link will be used to collect mobile daily diaries and videos of medication dosing, which are immediately transmitted into REDCap with de-identified subject IDs. Videos are uploaded and stored within REDCap, and not the user's device. Server maintenance will be conducted by Information Technology Specialists at MUSC. The PILSY platform will house PHI (email and phone number) that is necessary to setup a participant with a smart cap. PILSY has been vetted by MUSC IS and is approved to house data. The platform is password protected and only accessible by study team members.

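### Pregnancy triggers withdrawal from the study as well as from varenicline, so Week 12 outcomes that could still be collected are lost

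*Combined protocol and SAP*

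**What the plan says.** The pregnancy paragraph of Section 13.0 attaches two consequences to a pregnancy: "Participants who become pregnant during the trial will be instructed to discontinue study medication and withdrawn from the study". The wording is mandatory, and no later outcome assessment is mentioned there or elsewhere.

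The missing-data paragraph of Section 10.0, citing the intent-to-treat principle, says "we will make every effort to continue assessments for the entire course of treatment, even among those who stop participating in study procedures". It names no exception.

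Other reasons for stopping varenicline are handled differently. For intolerance of the reduced dose, Section 9.0 (Day 0) says "the medication will be discontinued, and the participant will continue to be tracked". For intolerable adverse events, Section 13.0 lets the participant "discontinue medication altogether, while remaining in the study for ongoing monitoring".

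Three further provisions bear on the point:

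- **Early termination (ET) visit.** Section 9.0 (Weekly Visits) says such a visit may take place when a participant wishes to leave, and adds "Week 12 assessments and procedures will be conducted for ET visits, should they occur".
- **Pregnancy tests.** Section 9.0 schedules them as "pregnancy [weeks 4, 8, 12, or as needed". The pregnancy paragraph of Section 13.0 says they are done at every visit.
- **Week 26.** Section 10.0 (Secondary Data Analysis) says "similar analytic models will be used to assess abstinence rates at the 6-month follow-up visit".

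**The concern.** Stopping the drug and leaving the study are separate decisions, and the plan treats them separately when varenicline is stopped for adverse events. On pregnancy it merges them. Varenicline is the only study drug, so stopping it already deals with the drug exposure. What remains for outcome collection is self-report and a urine sample.

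Followed as written, the rule creates missing outcomes that are not inevitable. A pregnancy found before Week 12 removes that participant's primary outcome, 7-day point prevalence abstinence at the end of treatment. Section 10.0 relies on maximum likelihood with ignorable attrition. Loss triggered by an event after baseline that may itself change smoking might not meet that assumption. Missing data produced by the protocol itself are the easiest kind to avoid.

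**Working it through.** **1. The texts side by side.** Section 10.0 promises continued effort through treatment, even for people who have stopped study procedures. Section 13.0 removes one group from the study altogether. The promise is a best-effort one, but the rule rules out the effort for that group. The promise covers only the treatment period, so the tension concerns Week 12 and not Week 26.

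**2. Whether the ET visit closes the gap.** It is optional and is described for people who wish to leave, whereas withdrawal for pregnancy is imposed. If an ET visit does follow, it takes place when the pregnancy is found. On the Section 9.0 test schedule, a positive test at Week 4 or Week 8 puts it 12 − 4 = 8 or 12 − 8 = 4 weeks before the endpoint. On the every-visit wording of Section 13.0, it could fall at any treatment week. Unless it falls in the Week 12 window, which the compensation paragraph of Section 9.0 does foresee, it does not measure the final 7 days of treatment.

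**3. Reach beyond Week 12.** After one week of titration, "Dosing of 2.0 mg per day will be maintained for the next 11 weeks", so the course ends at Week 12 (1 + 11). If the rule's time frame includes follow-up, a later pregnancy would cost the Week 26 outcome when no study drug is being taken.

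**4. The plan's sample size.** Inputs from Section 10.0 are 45% against 20% abstinence, 1:2 allocation, 80% power and 5% type 1 error (taken as two-sided). The pooled-variance formula for the smaller group is

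n = [1.96·√(p̄(1−p̄)·1.5) + 0.8416·√(p₁(1−p₁) + p₂(1−p₂)/2)]² / (p₁−p₂)², with p̄ = (0.45 + 2×0.20)/3 = 0.2833.

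This gives (1.0817 + 0.4816)²/0.0625 = 39.1, so 40 + 80 = 120, against the stated 41 + 82 = 123. Inflated for R² = 0.25 and 25% attrition, 120/(0.75×0.75) = 213, against the stated 208. Conversely, 208×0.75×0.75 = 117 effective participants give 79.9% power. The stated figures are close enough to stand. If 1, 3, 5 or 8 participants were lost beyond the 25% allowance, power would be 79.7%, 79.1%, 78.6% or 77.8%.

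**5. Possible size.** The documents give no pregnancy rate. I assume 1% and 2% of all participants, equal in both groups, with every loss before Week 12.

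- At 1%: 0.01×69 = 0.69 tobacco-only and 0.01×139 = 1.39 co-users, total 2.08. The attrition allowance is 0.25×208 = 52, and 2.08/52 = 4%.
- At 2%: total 4.16, and 4.16/52 = 8%.

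Let a be the share lost in each group, and x and y the abstinence rates among those lost in the tobacco-only and co-use groups. With observed outcomes only, gap = (0.45 − a·x)/(1−a) − (0.20 − a·y)/(1−a).

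| Those lost | a = 1% | a = 2% |
|---|---|---|
| Same rates as their group | 25.0 | 25.0 |
| All smoking, or all abstinent | 25.3 | 25.5 |
| Tobacco-only abstinent, co-users smoking | 44.44 − 20.20 = 24.2 | 43.88 − 20.41 = 23.5 |
| Tobacco-only smoking, co-users abstinent | 45.45 − 19.19 = 26.3 | 45.92 − 18.37 = 27.6 |

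These are raw percentage-point gaps, not estimates from the planned augmented inverse-probability-weighted model.

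**The case against.** The strongest reply is that Section 13.0 is a specific safety rule, while Section 10.0 states a general aspiration. A specific rule can limit a general one without contradicting it, and the entry criteria also keep pregnant people out of the whole study. That stands in part: a reader might infer a flat contradiction, and the documents do not force that. But no text declares the rule an exception, and reading it as one would not make the loss of the outcome necessary.

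A reader might also infer that the rule is inconsistent with the handling of people who stop varenicline for adverse events. It is not. Those provisions concern a different event and serve only as a comparison, showing that follow-up off drug is already part of this study.

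Loss of Week 26 outcomes might be taken as certain. The sentence can equally be read as applying to people still taking varenicline, so that reach is plausible but not established.

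The size calculation is illustrative. Only women can become pregnant and no sex split is given, so a rate r among all participants means r/f among women, where f is their share. Some pregnancies would also fall after Week 12 and could not affect the primary endpoint.

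Finally, withdrawal by the investigator under Section 12.0 might be thought to raise the same problem. It is discretionary and can be read together with Section 10.0, so no change is asked for there.

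**Conclusion.** The point holds as a minor, avoidable weakness. The pregnancy rule ends assessment where the plan otherwise undertakes to continue it during treatment, and so forfeits Week 12 outcomes that could still be collected. It forfeits Week 26 outcomes only on the wider reading of its time frame.

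The number affected is unknown. It is probably small, since Section 4.0 requires birth control and excludes anyone pregnant or contemplating pregnancy. Under the assumed 1% to 2%, it is about 2 to 4 people. Even with the most adverse outcomes, the planned 25-point gap then moves by at most about 1.3 points at 1% or 2.6 at 2%, in either direction.

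A reader might conclude that the primary comparison is biased or the study underpowered. The documents support neither: the direction of any bias is unknown, losses of this size fit within the 25% attrition allowance, and no stated sample-size or power figure is wrong.

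**What to change.** Amend the pregnancy paragraph of Section 13.0 so that pregnancy ends varenicline but, unless the participant withdraws consent, tobacco outcomes are still collected at Week 12 and Week 26. Section 9.0 already allows what is needed: remote visits, instant-read cotinine confirmed over video, and urine collected and frozen at home for later laboratory assay. The rule for stopping varenicline stays as it is.

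The cost is one reworded sentence, a few extra remote assessments (for about 2 to 4 participants under the assumed rates) and a little staff time. A matching change to the consent wording may be needed. That cannot be checked here, because the consent pages are not in the reviewed copy.
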